### 10.3 POPULATIONS FOR ANALYSES

Evaluable for toxicity: All patients will be evaluable for toxicity from the time of their first treatment with ONC201.

Evaluable for objective response: Only those patients who have measurable disease present at baseline, have received at least one cycle of therapy, and have had their disease re-evaluated will be considered evaluable for response. These patients will have their response classified according to the definitions stated below. (Note: Patients who exhibit objective disease progression prior to the end of cycle 1 will also be considered evaluable.)

Evaluable Non-Target Disease Response: Patients who have lesions present at baseline that are evaluable but do not meet the definitions of measurable disease, have received at least one cycle of therapy, and have had their disease re-evaluated will be considered evaluable for non-target disease. The response assessment is based on the presence, absence, or unequivocal progression of the lesions.

Evaluable for Progression Free Survival: In all three cohorts, all participants who took at least one cycle of study drug and have adequate follow-up to be included in a PFS analysis (cohort 1) or to have response and clinical benefit evaluated (cohorts 2 and 3) will be included in the analyses.

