 Labs must be obtained  $\leq 10$  days of initiating treatment: CBC with differential, PT/INR/PTT, sodium, potassium, chloride, carbon dioxide, BUN, creatinine or measured creatinine clearance, glucose, AST, ALT, bilirubin, calcium, total protein, albumin, alkaline phosphatase, phosphorus, magnesium, urinalysis, prolactin, estrogen, lactic acid and lipid panel. Lymphocyte phenotyping (TBNK). Urine or serum HCG for women of childbearing potential. Tumor Markers (CEA, CA15-3, CA27.29 for breast cancer and CA125 for endometrial cancer). Evaluation of germline BRCA1/2 (cohorts 1 and 2) or Lynch syndrome (germline evaluation) or MSI status of tumor (somatic evaluation by genomics, IHC or demonstration of Microsatellite instability of the tumor) (cohort 3) if no documentation of mutational analysis provided.

 Pathological confirmation of diagnosis (plus ER, PR and HER2 expression for breast cancer patients) in the Laboratory of Pathology at NIH Clinical Center or Walter Reed National Military Medical Center at Bethesda. However, if no pathologic specimen is available, patients may enroll with a pathologist's report showing a histologic diagnosis of HR+BC, TNBC or Endometrial Cancer in a College of American Pathologists (CAP) accredited laboratory and a clinical course consistent with the disease.

 Primary tumor paraffin block will be requested at enrollment to perform comparative genomic analysis as part of correlative studies planned for this clinical trial.

*Abbreviated Title: ONC201 in advanced cancers*

*Version Date: 06/17/2020*

 Planned biopsy after consent but prior to first dose of ONC201 as well as a planned biopsy on C2D2 after the 5th dose of ONC201. There is also an optional biopsy at the time of progression.

 Baseline images within 17 days prior to initiation of therapy: CT of chest/abdomen /pelvis (MRI may be substituted at investigator's discretion), Bone scan only at baseline. Brain MRI may be ordered at the discretion of the investigator if there is concern for CNS metastasis. CT of chest/abdomen/pelvis to be repeated every 8 weeks +/- 4 days after start of treatment (odd numbered cycles). Additional imaging to be performed at the investigator's discretion.

 12-lead EKG within 7 days prior to initiation of therapy and on C2D1, with monthly repeats only for abnormal baseline EKGs or if patient is symptomatic.

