**6.3.5 Progression-Free Survival**

PFS is defined as the duration of time from start of treatment to time of progression or death, whichever occurs first.

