### 10.4 STATISTICAL ANALYSES

#### 10.4.1 General Approach

Analyses performed will be descriptive, reporting the outcome measure indicated along with two-tailed 80% and 95% confidence intervals for PFS (cohort 1), and 80% and 95% confidence intervals about the response rate and clinical benefit rate in cohorts 2 and 3.

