#### 10.4.2 Analysis of the Primary Endpoints

Cohort 1: Kaplan-Meier curves for PFS using all patients who receive treatment and are eligible for evaluation will be included, and appropriate confidence intervals (80% and 95% two sided confidence intervals) at selected time points will be provided to help interpret results relative to the expected results.

Cohort 2 and 3: At the end of the trial we will form the two-sided 80% and 95% CI about the observed percentages of both response (PR+CR) and clinical benefit (SD+PR+CR).

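### Section 10.3 takes treated patients with no re-evaluation out of ORR and CBR, permits cycle-1 events to be left out of cohort 1 PFS, and contradicts itself on cycle-1 progressors

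*Combined protocol and SAP*

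**What the plan says.** Section 6.3.5 starts the PFS clock at first treatment: "PFS is defined as the duration of time from start of treatment to time of progression or death, whichever occurs first".

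Section 10.3 then gives two evaluability rules.

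- **Response paragraph.** It is restricted to patients with measurable disease at baseline who "have received at least one cycle of therapy, and have had their disease re-evaluated will be considered evaluable for response". A Note adds one exception: "Patients who exhibit objective disease progression prior to the end of cycle 1 will also be considered evaluable".
- **Last paragraph, headed as the PFS population.** It covers "all participants who took at least one cycle of study drug and have adequate follow-up to be included in a PFS analysis" for cohort 1, and continues "or to have response and clinical benefit evaluated (cohorts 2 and 3) will be included in the analyses". It has no exception for early events and does not say what a cycle taken or sufficient follow-up means.

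Section 10.4.2 describes the cohort 1 analysis as "Kaplan-Meier curves for PFS using all patients who receive treatment and are eligible for evaluation will be included", which leads back to section 10.3. Section 10.4.1 sets the tone: "Analyses performed will be descriptive, reporting the outcome measure indicated". Section 10.2 counts 24, 29 and 25 as evaluable patients, applies the cohort 2 and 3 stopping rules to the first 10 and 13 evaluable patients, and sets a ceiling of 90 to leave room for a few unevaluable ones.

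**The concern.** Being evaluable depends on what happens after treatment starts, and early failure is a main reason for not being evaluable.

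In cohort 1, a patient who progresses or dies before finishing the 28-day first cycle has a valid event under section 6.3.5 but does not meet the one-cycle condition of section 10.3. Leaving such patients out raises the PFS curve.

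In cohorts 2 and 3, a treated patient who dies, deteriorates, stops or withdraws before any re-evaluation has no recorded response. Removing that patient can only raise ORR and CBR. It also makes the futility stops less likely, because those rules wait for evaluable patients.

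The two paragraphs also disagree. A cohort 2 or 3 patient with objective progression in cycle 1 is evaluable under the Note and fails the one-cycle condition of the last paragraph, although both govern response.

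**Working it through.** **1. The plan's own figures reproduce.**

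- Cohort 1 (section 10.2: n = 24, median 4 v 8 months, one-sided 0.10). Test S(4) = 0.50. With exponential PFS the alternative is S(4) = 2^(-0.5) = 0.707. Null SE = 0.5/√24 = 0.102; alternative SE = √(0.707 × 0.293/24) = 0.093. Power = Φ((0.707 − 0.5 − 1.2816 × 0.102)/0.093) = 79.4%, against 80% stated.
- Cohort 2: P(X ≥ 11 | 29, 0.45) = 82.9%, against 82% stated. The exact 80% interval for 11/29 is 25.7–51.5%, as stated.
- Cohort 3: P(X ≥ 4 | 25, 0.25) = 90.4%, against 90% stated.

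**2. Exclusion share.** Let e be the share of treated patients excluded. The documents give no expected value, so 2%, 5% and 10% are assumptions. The ceiling gives an upper reference: 24 + 29 + 25 = 78; 90 − 78 = 12; 12/90 = 13.3%.

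**3. Effect on the benchmarks.** Assume the null rate p0 describes all treated patients and that no excluded patient is a success. The rate among evaluable patients is then p0/(1 − e).

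| Excluded | Cohort 2: P(≥11/29), p0 = 25% | Cohort 3: P(≥4/25), p0 = 5% | Cohort 1: P(≥16/24 progression-free at month 4), p0 = 50% |
|---|---|---|---|
| 0 | 8.6% | 3.4% | 7.6% |
| 2% | 9.6% | 3.6% | 9.1% |
| 5% | 11.5% | 4.0% | 12.0% |
| 10% | 15.5% | 4.7% | 18.7% |
| 13.3% | 18.9% | 5.3% | not shown |

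Worked line, cohort 2 at 5%: 0.25/0.95 = 0.263, and P(X ≥ 11 | 29, 0.263) = 11.5%.

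The cohort 1 cutoff is illustrative; the plan states none. It is the smallest count for which z = (p − 0.5)/√(p(1 − p)/24) exceeds 1.2816, where p is the observed proportion: 16/24 gives z = 1.73, and 15/24 gives 1.26. It assumes no censoring before month 4. In this column e is the share of patients with a documented early event who are left out. The 13.3% allowance covers any reason for being unevaluable, so it is not applied here.

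**4. Adding patients back.** In cohort 2, 11/29 has an 80% lower limit of 25.7%. One unassessed patient added (11/30) gives 24.8%, below 25%. In cohort 3, 4/25 has a lower limit of 7.2%, and even 4/28 keeps 6.4%, above 5%.

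**5. Stopping rules.** The true CBRs here are assumptions. Cohort 2, CBR 25%: P(X ≤ 1 | 10) falls from 24.4% to 23.3%, 21.6% and 18.7% at 2%, 5% and 10% excluded. Cohort 3, CBR 10%: P(X = 0 | 13) falls from 25.4% to 24.7%, 23.6% and 21.6%.

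**The case against.** **Cohort 1 wording.** A reader might infer that section 10.3 orders every cycle-1 event to be dropped. It does not. Unlike the response paragraph, the last paragraph is phrased as who will be included, without the word only, and a documented death or progression can reasonably count as enough follow-up. The harm is confined to documented early events: a living patient with no scan, if censored at day 1, leaves the Kaplan-Meier curve as it would be without that patient. Scheduled imaging starts at 8 weeks, so progression documented within 28 days would mostly need an unscheduled scan. This stands, and it is why the charge is that the text permits exclusion.

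**Early failures in cohorts 2 and 3.** A reader might infer that all of them disappear from ORR. They do not: the Note keeps objective cycle-1 progressors. Section 3.4 also allows more scans ("Additional imaging to be performed at the investigator's discretion"), and section 6.3.3.3 asks for progression to be documented even after treatment ends. These reduce the number lost but leave the rule unchanged.

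**Planned replacement.** The ceiling of 90 shows that unevaluable patients were foreseen. Replacing them does not count them, so the direction of the bias remains.

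**Descriptive analyses.** Reaching a benchmark is not a formal rejection, so the percentages above do not show a broken error rate. The 11/30 result occurs only at exactly 11 responders; 12/30 has a lower limit of 27.7%. The plan also calls 3/25 in cohort 3 potentially worth pursuing with a lower limit of 4.5%, below its 5% null. All of this stands.

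**Reference population.** If the null rates describe evaluable patients, the inflation in the table vanishes. The documents do not say which applies.

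**Conclusion.** The point holds as a defect of the analysis-population wording; no stated design figure is wrong. For ORR and CBR the exclusion of unassessed treated patients is explicit and can only favour the drug. For cohort 1 PFS the text permits, and does not require, leaving out events that section 6.3.5 counts. The contradiction over cycle-1 progressors needs resolving whatever the size of the bias.

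The size is moderate in cohort 2 (8.6% to 11.5% at 5% excluded, 18.9% at the full allowance) and small in cohort 3 (at most 5.3%). In cohort 1 it depends on an illustrative cutoff and on documented early events only. These figures rest on assumed exclusion shares and on null rates that refer to all treated patients. Because the analyses are descriptive, the consequence lies in how the 80% intervals and the benchmarks are read, and it is zero if nobody is excluded.

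A reader might also infer that the trial must be enlarged or redesigned. The documents do not support that: the defect is repaired by wording, and the ceiling leaves 12 places. It should be fixed because it is cheap to fix and acts in one direction.

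**What to change.** In sections 10.3 and 10.4.2:

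- **Cohort 1 PFS.** Include every eligible patient who received at least one dose. Count every documented progression or death from first dose, cycle 1 included.
- **ORR, CBR and the cohort 2 and 3 stopping rules.** Count treated patients without a post-baseline assessment as not responding and without clinical benefit. Compute exact intervals on the treated denominator.
- **Evaluable set.** Keep it as a sensitivity analysis. Define the one-cycle and follow-up conditions, carry the Note into the last paragraph of section 10.3 and extend it to deaths, and report how many patients are excluded.

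In section 10.2, say that the basis changes from evaluable to treated patients and restate power. If the sponsor prefers to keep 24, 29 and 25 as evaluable numbers, the 12 spare places already allow it.

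**Cost.** No new data; estimates may look slightly less favourable. If 29 and 25 become treated patients, 5% are unassessed and the planned effect holds only in assessed patients, power falls as follows:

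- cohort 2, P(X ≥ 11 | 29, 0.45 × 0.95 = 0.4275): 82.9% to 76.0%;
- cohort 3, P(X ≥ 4 | 25, 0.25 × 0.95 = 0.2375): 90.4% to 87.8%.

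There is no loss if the planned effects already refer to all treated patients. No cohort 1 power cost is given, because it would rest on a cutoff and an early-event model that the plan does not state.

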### 10.4 STATISTICAL ANALYSES

#### 10.4.1 General Approach

Analyses performed will be descriptive, reporting the outcome measure indicated along with two-tailed 80% and 95% confidence intervals for PFS (cohort 1), and 80% and 95% confidence intervals about the response rate and clinical benefit rate in cohorts 2 and 3.

#### 10.4.2 Analysis of the Primary Endpoints

Cohort 1: Kaplan-Meier curves for PFS using all patients who receive treatment and are eligible for evaluation will be included, and appropriate confidence intervals (80% and 95% two sided confidence intervals) at selected time points will be provided to help interpret results relative to the expected results.

Cohort 2 and 3: At the end of the trial we will form the two-sided 80% and 95% CI about the observed percentages of both response (PR+CR) and clinical benefit (SD+PR+CR).

#### 10.4.3 Analysis of the Secondary Endpoints

- Cohort 1 HR+BC – Safety—AEs will be tabulated, ORR—response rate will be reported along with 95% two-sided confidence interval, clinical benefit rate (CBR; CR + PR + SD

*Abbreviated Title: ONC201 in advanced cancers*

*Version Date: 06/17/2020*

by RECIST) clinical benefit rate will be reported along with 95% two-sided confidence interval

- Cohort 2 TNBC – Safety-AEs will be tabulated CBR, clinical benefit rate will be reported along with 95% two-sided confidence interval; PFS by Kaplan-Meier analysis
- Cohort 3 Endometrial Cancer – Safety, CBR clinical benefit rate will be reported along with 95% two-sided confidence interval, PFS by Kaplan-Meier analyses

#### **10.4.4 Safety Analyses**

The safety of ONC201 tabulations be evaluated by descriptive statistics of each adverse event type and grade.

#### **10.4.5 Baseline Descriptive Statistics**

No formal analysis of baseline statistics will be performed.

#### **10.4.6 Planned Interim Analyses**

The interim analyses are described for each cohort in the sample size determination paragraph.

#### **10.4.7 Sub-Group Analyses**

No subgroup analyses are planned.

#### **10.4.8 Tabulation of individual Participant Data**

No individual participant data will be provided.

#### **10.4.9 Exploratory Analyses**

Blood samples at baseline and Day 1 of each subsequent cycle, as well as biopsy specimens at baseline and cycle 2 will yield a set of biomarkers, such as markers of apoptosis, indications of mitochondrial damage and immune subsets. The difference of the values at cycle 1 vs. baseline and cycle 2 vs. baseline will be determined, and these differences will be used as a covariate for analysis of PFS in each cohort to see if the level of change in biomarkers may be associated with PFS. These analyses will be done in an exploratory fashion using Kaplan-Meier curves and log rank tests. The changes in the biomarkers will also be compared between responders and non-responders in the three cohorts using an exact form of a Wilcoxon rank sum test. All of these explorations will be done only if adequate patient data are available. Results will be presented without adjustment for multiple comparisons.

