##### 5.4.1 **Timing**

Research blood samples will be performed at the following times:

- C1D1: after consent, prior to treatment on cycle 1 day 1
- C1D1: 6 hours after ONC201 administration (blood for PK only)
- On Day 1 of each cycle starting with cycle 2: Prior to treatment on day 1
- Optional - at the time of progression

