### 15.3 APPENDIX C – SOP FOR CYTOKINE COLLECTION

#### Appendix C -

##### **Time points of the sampling**

- Venous blood should be collected from all patients enrolled in the protocols at the beginning of therapy, prior to the administration of the investigational agent. The pre-cycle 1 samples will serve as the baseline sample. Additional time points should be defined in the clinical protocol.

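### Section 10.4.9 tests a continuous biomarker change against PFS by log-rank with no grouping rule, and its cycle 1 difference has no matching on-treatment draw in Section 5

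*Combined protocol and SAP*

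**What the plan says.** Section 10.4.9 (Exploratory Analyses) defines two contrasts: "The difference of the values at cycle 1 vs. baseline and cycle 2 vs. baseline will be determined". It then says that "these differences will be used as a covariate for analysis of PFS in each cohort", to see whether the level of change is associated with PFS. The method follows: "These analyses will be done in an exploratory fashion using Kaplan-Meier curves and log rank tests". No regression model, cut-point or number of groups is stated. The same section compares the changes between responders and non-responders with an exact Wilcoxon rank sum test, which needs no cut. It makes all of this conditional on adequate data and applies no multiplicity adjustment.

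On sampling, Section 10.4.9 itself lists "Blood samples at baseline and Day 1 of each subsequent cycle", with biopsies at baseline and cycle 2. Section 5.4.1 gives the research blood times as "C1D1: after consent, prior to treatment on cycle 1 day 1"; a second C1D1 draw, "6 hours after ONC201 administration (blood for PK only"; then "On Day 1 of each cycle starting with cycle 2: Prior to treatment on day 1"; and an optional draw at progression. The cytokine procedure in Appendix C adds: "The pre-cycle 1 samples will serve as the baseline sample".

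**The concern.** There are two gaps.

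- **Grouping.** Calling the change a covariate suggests a regression, but the named tests compare groups. Two analysts who follow the text could cut the same marker at different points and report different results. Even the natural choice, a median split, discards information that cohorts of 24 to 29 can ill afford.
- **Time point.** One of the two planned contrasts is labelled cycle 1 versus baseline, yet the sampling sections make the cycle 1 biomarker sample the baseline. The analyst has to guess which sample is meant.

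Finding candidate predictive biomarkers is the stated main aim of the correlative work (Sections 1.1.3 and 5.1), and patients have two mandatory biopsies partly for this purpose. The stake is how much that material can yield. No decision rule of the trial depends on it.

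**Working it through.** **1. Is there a plan figure to reproduce?** No. Section 10.4.9 states no sample size, error level, power or cut-point.

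**2. Cost of cutting at the median (illustration).**

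Inputs from Section 10.2:
- cohort sizes 24, 25 and 29;
- the 4-month median PFS of Cohort 1;
- follow-up of 12 to 36 months (1 year after the last patient starts, plus 2 years of accrual in Cohort 1).

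Assumptions: the Cohort 1 median and follow-up are applied to all three sizes; change normally distributed; PFS exponential; hazard ratio 1.65 or 2.0 per SD of change; two-sided 5%; a value for every patient; 4,000 simulated cohorts per setting.

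The test statistic is Z = U/√V. U sums, over events, the patient's x minus the mean x of those at risk. V sums the variance of x among those at risk. With x continuous this is the Cox score test. With x replaced by an above/below-median indicator it is the log-rank test. Only the cutting differs between the two.

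| n | HR per SD | Median split | Continuous | Difference (points) |
|---|---|---|---|---|
| 24 | 1.65 | 39.6% | 56.1% | 16.5 |
| 24 | 2.0 | 58.6% | 80.2% | 21.6 |
| 25 | 1.65 | 39.3% | 56.6% | 17.3 |
| 25 | 2.0 | 60.2% | 80.9% | 20.7 |
| 29 | 1.65 | 45.8% | 64.0% | 18.2 |
| 29 | 2.0 | 69.1% | 88.1% | 19.0 |

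With no association, rejection rates are 6.0 to 6.1% for the median split and 5.5 to 6.5% for the continuous test, so the gain is not bought with a higher error rate.

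Plausibility check: splitting a normal variable at its median keeps about 2/π = 0.64 of the information, so the expected Z shrinks by √(2/π) = 0.798. At n = 24 and HR 2.0, 80.2% power means an expected Z of 1.96 + 0.849 = 2.809. Then 2.809 × 0.798 = 2.241, and Φ(2.241 − 1.96) = 61%, against 58.6% simulated. At HR 1.65 the same steps give 39%, against 39.6%.

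**3. Which samples support the cycle 1 contrast?**

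| Source | On-treatment biomarker sample in cycle 1? |
|---|---|
| Section 10.4.9 | None listed: blood at baseline and Day 1 of later cycles; biopsy at baseline and cycle 2 |
| Section 5.4.1 | None: C1D1 pre-dose; the 6-hour draw is PK only; next draw at C2D1 pre-dose |
| Table 5 (M30/M65, TRAIL, CTC and cell-free DNA, cytokines, immune assays) | None: C1D1 pre-treatment, then Day 1 of later cycles |
| Section 5.3.1 | None: biopsies before treatment and at C2D2 |
| Appendix C | Pre-cycle 1 sample is the baseline |
| Study calendar (Section 3.4) | Marks at Screening/Baseline and at C1D1; Section 5.4.1 places the C1D1 biomarker draw before dosing |
| Appendix F specimen log | Yes: serum 6 hours after the first dose |

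Only Appendix F supplies a candidate. It is limited to serum, so it cannot serve the blood-cell, circulating-tumor-cell or biopsy markers.

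**4. Patients lost when the clock starts at the sample.** Under exponential PFS with a 4-month median, the fraction with an event by time t (months) is 1 − 2^(−t/4).
- C2D1: 28/30.4 = 0.92 months, so 1 − 2^(−0.230) = 15%, leaving about 20 of 24.
- C3D1: 56/30.4 = 1.84 months, so 1 − 2^(−0.460) = 27%.

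The first scheduled scan is at 8 weeks, so fewer than 15% may have a documented progression before C2D1.

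**The case against.** The strongest reply is that this is an exploratory paragraph, conditional on adequate data, from which no stopping rule or primary conclusion follows. A median split fixed in advance is compatible with the text, and the Wilcoxon comparison already uses the changes uncut. Cox regression adds proportional-hazards and log-linearity assumptions in a very small sample. All of that stands, and it keeps the importance low. It does not supply the missing rule or define the time point.

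Three stronger readings are tempting, and the documents do not support them.

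- **A reader might infer that no cycle 1 on-treatment sample exists, so that the difference is zero by construction.** That is true of Sections 5.3.1 and 5.4.1 and Table 5, but the Appendix F log lists a 6-hour serum specimen, and the Appendix F summary mentions serum tumor biomarkers. Cycle 1 could also mean the end of cycle 1, that is the C2D1 draw. However, Section 10.4.9 uses cycle 2 for the C2D2 biopsy, so the label stays ambiguous.
- **A reader might infer a heavily inflated false-positive rate.** In the same simulation, taking the best of 13 cuts between the 20th and 80th percentiles rejects 29.0 to 30.5% of the time with no association. The plan proposes no such search. The figure shows why a cut should be fixed and does not describe this analysis.
- **A reader might infer that counting PFS from treatment start biases the comparison.** Everyone compared must have reached the sample, and with a common sample time the risk sets after it are the same. The effect is on the plotted curves and medians, which include about 28 event-free days.

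**Conclusion.** The point holds as a low-importance improvement. Section 10.4.9 leaves the grouping for its log-rank tests unspecified. The most natural choice, a median split, costs 16.5 to 21.6 points of power against the continuous test in the six scenarios examined. Those figures rest on assumed effect sizes, normal changes, exponential PFS and a biomarker value in every patient from time zero. They compare two tests on the same patients and are not the power to expect in the trial. Sections 1.1.3 and 5.1 limit correlative work to select patients with adequate samples, and early events reduce the number further.

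Separately, the cycle 1 versus baseline contrast has no matching on-treatment biomarker draw in the sampling sections, and Appendix F conflicts with Section 5.4.1 about the 6-hour specimen. The documents do not settle which is intended.

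**What to change.** In Section 10.4.9:

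1. Make Cox regression on the continuous change the stated analysis, reported as a hazard ratio per SD with a confidence interval. Count time from the on-treatment sample in patients still at risk.
2. Keep Kaplan-Meier curves at a median split fixed in advance, for display only.
3. Define the differences as C2D1 minus C1D1 pre-dose for blood, and C2D2 minus baseline for biopsies.
4. Reconcile Sections 5.4.1 and 10.4.9 with the Appendix F log: either the 6-hour serum specimen is a biomarker sample with a stated use, or the log should not list it.

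The cost is protocol and SAP wording; the proposed differences use samples already planned. The downsides are a proportional-hazards, log-linear assumption in a small exploratory model, and the exclusion of patients with an event before the sample (up to about 15% at C2D1 under the assumptions above). Most of those patients would have no on-treatment value under the present text either, since progression ends protocol therapy. A further C3D1 contrast is possible but would lose about 27%.
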